#### 4.7 Testing Schedule

[Table 1](#) presents the assessments to be completed by study timepoint. See [Appendix III](#) for a description of the study instruments. The assessments should be administered in the order listed in [Table 1](#).

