The design will be a single-blind, dose-controlled trial in which half of the participants will be randomized to the adaptive intervention condition and half will complete training on a non-adaptive comparison computer program. At each assessment (baseline, post-treatment, and follow-up), the person performing any cognitive testing (i.e., computerized assessment and/or the optional psychologist battery) will be blinded to randomization. Given the role of cognitive-behavioral coaching in the CT program, it will not be possible for coaches to be blinded to participants' randomization status, but coaches will not perform any of the pre- or post-training assessments. In our previous work, we had no difficulty maintaining this blind between coaches and examiners. Parents and participants will be blinded to randomization, at least initially. Because they will have been informed that the two study conditions are distinguished by their difficulty level, some parents and/or children may be able to guess their randomization status. Reminder: if patient starts or changes dosage of psychostimulant medications during the study period, patient will be removed off study.

*Cogmed* (see [Appendix II](#)) is a home-based, computerized, interactive, audio-visual CT program. Designed to be completed over 25 training sessions spanning 5-9 weeks, *Cogmed* consists of twelve engaging exercises that target skills involving visuo-spatial and verbal WM (separate versions of the program are available for preschool- and school-aged children). This CT program is particularly appropriate for the pediatric brain tumor population because of its ease-of-use, ability to be completed at home, and established efficacy in other patient

populations. Primary outcomes will include measures of attention and WM. Of note, participants assigned to the non-adaptive condition will complete a modified version of the computerized CT consisting of tasks that never increase in difficulty. If patients do not complete the training within 9 weeks, they will be removed off protocol therapy (see [Section 5.1](#)).

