#### 4.6 Feasibility Interview

For a previous trial with survivors of childhood cancer (R03-CA132570), a 13-item survey (see [Appendix VA](#) and [VB](#)) for parents and children was developed and utilized to assess technical feasibility, adherence, satisfaction, and ease-of-use. The Feasibility Interview will be completed by the parent by phone following Session 12. Additionally, both child and parent will complete a second interview during the post-intervention assessment. See [Table 1](#) below.

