**Table 1: Testing Schedule**

Testing Session	Child	Parent
Baseline	

- CogState

Optional (psychologist-administered) measures:

- WISC-V (Block Design, Vocabulary, Digit Span, Coding, Symbol Search, and Spatial Span subtests)

- CMS (Dot Location and Faces subtests)

- CVLT-C

- Instructional WM

	

- Socioeconomic Status Measure

- Computer Use Questionnaire

- COG Language Questionnaire

- BASC-3

- BRIEF

- ABAS-3

- BIS

Following CT Session 12		

- Feasibility Interview

Post-Intervention	

- Feasibility Interview

- CogState

Optional (psychologist-administered) measures:

- WISC-V (Digit Span, Coding, Symbol Search, and Spatial Span subtests)

- CMS (Dot Location and Faces subtests)

- Instructional WM

	

- Feasibility Interview

- BRIEF

6-Month Follow-Up	

- CogState

Optional (psychologist-administered) measures:

- WISC-V (Digit Span, Coding, Symbol Search, and Spatial Span subtests)

- CMS (Dot Location and Faces subtests)

- CVLT-C

- Instructional WM

	

- Computer Use Questionnaire

- BRIEF

- ABAS-3

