### 6.0 STATISTICAL CONSIDERATIONS

#### 6.1 Statistical Design

This primary goal of the study is to establish feasibility of a home-based computerized cognitive training program *Cogmed*, on patients 6 to 16 years of age with pediatric brain tumors and undergoing CRT. Within approximately 2-4 months of completing CRT, patients meeting criteria for randomization will be randomized 1:1 to Arm A the intervention arm (adaptive program) or Arm B the active control arm (non-adaptive program). Randomization will be stratified by known risk factors including age (< 8 years vs.  $\geq$  8 years), treatment intensity (whole brain vs. focal RT) and also by Coach (A versus B). Randomized patients are expected to complete 25 training sessions over 5 to 9 weeks, and then complete a post-

intervention testing and a 6-month follow-up testing. The treating psychologist and/or the individual performing computerized cognitive testing must be blinded for testing.

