## APPENDIX VB: CHILD FEASIBILITY AND ACCEPTABILITY INTERVIEW

### Obtain After Training Completion

Subject: \_\_\_\_\_

Subject ID: \_\_\_\_\_

Date: \_\_\_\_\_

1. Using the following scale, how often did you feel frustrated while using the computer program?

- Never
- Rarely
- Sometimes
- Often
- Always

2. Using the following scale, how often did you feel bored during the computer exercises?

- Never
- Rarely
- Sometimes
- Often
- Always

3. Using the following scale, how often did you enjoy the computer exercises?

- Never
- Rarely
- Sometimes
- Often
- Always

Comments:

---

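### The Table 1 order at the post-intervention visit puts the child's interview about the training before the blinded cognitive testing, an avoidable risk to the tester's blind

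*Combined protocol and SAP*

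**What the plan says.** Section 4.7 introduces Table 1 and adds: "The assessments should be administered in the order listed in" that table. In the child column of the post-intervention row the sequence begins "Feasibility Interview - CogState", and the optional psychologist-administered tests follow. Section 4.6 places the interview within the same visit: "both child and parent will complete a second interview during the post-intervention assessment".

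The child's form (Appendix VB) has three frequency items and a comments field. The first item asks "how often did you feel frustrated while using the computer program"; the other two concern boredom and enjoyment.

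On blinding, Section 4.1 says that at each assessment "the person performing any cognitive testing (i.e., computerized assessment and/or the optional psychologist battery) will be blinded to randomization". Section 6.1 repeats the rule for the treating psychologist and/or the "individual performing computerized cognitive testing must be blinded for testing". Section 4.1 also explains that, because families have been told "the two study conditions are distinguished by their difficulty level, some parents and/or children may be able to guess their randomization status".

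**The concern.** What separates the arms is how hard the training becomes: it adapts upward in Arm A and stays flat in Arm B. A child talking about the training may say that it kept getting harder, or that it was always the same. The plan asks the child to talk about the training, and allows free comments, immediately before the tests whose examiner must not know the arm.

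The plan accepts that families may guess, so the tester's blind is an important protection for the tests that a person administers. Those tests feed the exploratory objective in Section 1.2: an effect size on attention and working memory to be used in designing a definitive trial. A tester who learns the arm at this visit could also test the same child at 6 months.

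**Working it through.** The plan gives no figure on this point, so the check compares the relevant sections.

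1. **Order.** Section 4.7 asks sites to follow Table 1, and Table 1 puts the child's interview first at the post-intervention visit. The verb is should, so this is an instruction without the force of an absolute requirement.

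2. **Who gives the interview.** The documents do not say who gives it at the visit. Section 4.1 bars the coaches, who know the arm, from the pre- and post-training assessments. Section 4.5.3 lets anyone with the online training administer CogState. One site staff member could therefore conduct the interview and then the testing without departing from any written instruction on roles.

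3. **Existing safeguards.** Sections 4.1 and 6.1 state the blinding rule, but neither says how it is kept when the child describes the training. Section 4.1 reports no earlier difficulty in keeping the blind, but this refers to coaches and examiners, not to what a child tells an examiner.

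4. **What the interview can reveal.** None of the three items in Appendix VB asks about difficulty, so the clue is indirect: boredom, frustration or a spontaneous comment. The parent's form (Appendix VA) asks directly how easy or hard the exercises were, and it too comes first in its column. A tester within earshot of either interview could pick up a hint.

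5. **Which outcomes are exposed.**
   - Primary endpoint (Section 6.3.1): sessions completed within 9 weeks. Appendix II says the program logs sessions automatically, so this is not exposed.
   - CogState Groton Maze Learning and one-back tasks: uploaded and scored automatically (Appendix III). A tester could influence them only through proctoring.
   - Digit Span, Spatial Span and Dot Location: secondary endpoints administered by an examiner, so this is the main exposure. They are optional by site, so the number of children is an unknown part of the target of 60.

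6. **Which visits.** The child's interview occurs only at the post-intervention visit, so the order problem is confined to it. Table 1 lists no interview at 6 months, although Section 4.5.3 can be read as asking the parent for one then as well. Anything a tester learns at the first visit can carry over to the second.

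7. **How much testing would come before the interview if it moved to the end.** Section 4.5.3 gives 20–30 minutes for the core testing and about 30 more for the psychologist-administered part. Without the optional tests the wait is 20–30 minutes; with them it is 20 + 30 = 50 to 30 + 30 = 60 minutes. The overall range is 20–60 minutes.

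**The case against.** The strongest reply is that the blinding rule governs. A site can follow the Table 1 order and still keep the blind by having someone else conduct the interview; Appendix VA itself names the coach, the psychologist and the research assistant as separate members of the study team. On this view the gap is an unassigned interviewer, not the order. Much of this stands: a breach occurs only if the tester gives or hears the interview, and the documents do not say that this happens. But the plan prescribes a sequence that works against its own blinding rule and does not tell sites to separate the roles.

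A second reply is that the child's answers are weak evidence of the arm, since children in either arm could be bored or frustrated over 25 sessions. That also stands, and it limits the concern to a hint.

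A third reply is that placing the interview first may protect it. Satisfaction and ease of use belong to the primary hypothesis in Section 1.1, while the cognitive effect sizes are exploratory. An interview after testing might be coloured by fatigue, or by confusion between CogState and the training program. This is a real cost but a small one for a three-item form, and a sentence from the interviewer addresses the confusion.

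Finally, reordering alone would not stop a tester who hears the interview afterwards from carrying the knowledge to 6 months. That is correct, and it is why the fix also covers who gives the interviews and who can hear them.

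**Conclusion.** The point holds as an avoidable risk to the tester's blind at the post-intervention visit, with possible carry-over to 6 months. It bears mainly on the optional examiner-administered secondary measures. It assumes that at some sites the tester gives or overhears an interview, which the documents neither state nor rule out. The size of any bias cannot be derived from them.

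A reader might infer more than the documents support:

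- **That the order is mandatory and breaks the blind for all 60 or so children.** The wording is should, and no breach is shown.
- **That the objective outcomes as a whole are compromised.** CogState is scored automatically, and the primary compliance endpoint is logged by the program.
- **That recalling frustration or boredom shifts test performance differently by arm.** Nothing in the documents bears on this.

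This is a cheap improvement to a feasibility pilot and does not threaten its primary conclusion.

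**What to change.** In the post-intervention row of Table 1, list the child's Feasibility Interview after CogState and all psychologist-administered tests.

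Add to Section 4.6 that the child and parent interviews are given out of the blinded tester's hearing, where available by existing site staff other than that tester, and not by the coach. This second part is what protects the 6-month visit, and it also covers the parent's direct question about difficulty.

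Add one line for the interviewer to say to the child: the questions are about the home training program, not the CogState session just finished.

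The cost is one reordered table cell and two sentences, with no new assessment and no added testing time. The downside is that the child rates the training after 20–60 minutes of testing. A site with only one available staff member may be unable to separate the roles; there, moving the interview to the end still protects the post-intervention tests but not the 6-month visit.

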**Table 1: Testing Schedule**

Testing Session	Child	Parent
Baseline	

- CogState

Optional (psychologist-administered) measures:

- WISC-V (Block Design, Vocabulary, Digit Span, Coding, Symbol Search, and Spatial Span subtests)

- CMS (Dot Location and Faces subtests)

- CVLT-C

- Instructional WM

	

- Socioeconomic Status Measure

- Computer Use Questionnaire

- COG Language Questionnaire

- BASC-3

- BRIEF

- ABAS-3

- BIS

Following CT Session 12		

- Feasibility Interview

Post-Intervention	

- Feasibility Interview

- CogState

Optional (psychologist-administered) measures:

- WISC-V (Digit Span, Coding, Symbol Search, and Spatial Span subtests)

- CMS (Dot Location and Faces subtests)

- Instructional WM

	

- Feasibility Interview

- BRIEF

6-Month Follow-Up	

- CogState

Optional (psychologist-administered) measures:

- WISC-V (Digit Span, Coding, Symbol Search, and Spatial Span subtests)

- CMS (Dot Location and Faces subtests)

- CVLT-C

- Instructional WM

	

- Computer Use Questionnaire

- BRIEF

- ABAS-3

#### 4.8 Feedback to Participants

The study psychologist at each site will inform the health care providers of participants who receive scores in the bottom 7% (i.e., 1.5 SD below the mean) relative to the standardization sample on the WISC-V estimated IQ, WISC-V Working Memory Index, WISC-V Processing Speed Index, or the BRIEF Metacognitive or Behavioral Regulation Indices, given that extreme scores on these measures may reflect significant difficulties that can interfere with learning. When children receive scores at or more extreme than 1.5 SD from the mean, their health care team will be informed of the results in the form of a letter listing the scores of concern. In this way, the health care team can follow up with families to determine if further assessment is warranted based on whether or not families are observing difficulties in their child's functioning at home or in school, and make a referral as they would normally do when families report concerns of this kind.

**This feedback requirement will not apply to sites that are not completing the optional psychologist-administered portion of the testing visits.**

### 5.0 CRITERIA FOR REMOVAL FROM PROTOCOL THERAPY AND OFF STUDY CRITERIA

#### 5.1 Criteria for Removal from Protocol Therapy

- a) Refusal of further protocol treatment by patient/parent/guardian.
- b) Completion of planned study treatment.
- c) Physician determines it is in patient's best interest.
- d) Patient does not complete the computerized cognitive training within 9 weeks.
- e) Development of seizures or change in functional status that will prevent patient from completing further treatment or assessments.
- f) Progressive disease or relapse

#### 5.2 Off Study Criteria

- a) Death
- b) Lost to follow-up (prior to 6-month follow-up testing)
- c) Completion of all study assessments.
- d) Withdrawal of consent for any further data submission.
- e) Patient did not meet criteria to proceed to randomization.
- f) Patient is started on psychostimulant medications or change in dose of psychostimulant medication.
- g) Patient refuses randomization

### 6.0 STATISTICAL CONSIDERATIONS

#### 6.1 Statistical Design

This primary goal of the study is to establish feasibility of a home-based computerized cognitive training program *Cogmed*, on patients 6 to 16 years of age with pediatric brain tumors and undergoing CRT. Within approximately 2-4 months of completing CRT, patients meeting criteria for randomization will be randomized 1:1 to Arm A the intervention arm (adaptive program) or Arm B the active control arm (non-adaptive program). Randomization will be stratified by known risk factors including age (< 8 years vs.  $\geq$  8 years), treatment intensity (whole brain vs. focal RT) and also by Coach (A versus B). Randomized patients are expected to complete 25 training sessions over 5 to 9 weeks, and then complete a post-

intervention testing and a 6-month follow-up testing. The treating psychologist and/or the individual performing computerized cognitive testing must be blinded for testing.

## 6.2 Patient Accrual and Expected Duration of Trial

The study accrual target is 60 randomized patients evaluable for the primary endpoint of intervention compliance. It is anticipated that some children who complete the baseline assessment will not meet the eligibility criteria for randomization based on evidence of intellectual disability or psychiatric functioning. In the trial of *Cogmed* with survivors, less than 10% of children screened were excluded from participation for these reasons.

Randomized patients who are removed off protocol therapy for medical reasons (relapse/progression, death, physician's determination in the patient's best interest, development of seizures or other change in functional status, or starting or changing the dose of psychostimulants) would be deemed inevaluable for the primary compliance endpoint. Therefore, using an estimate of 15% for screen failures and inevaluable patients, we project that we may need to enroll up to 71 participants.

With enrollment open to all institutions within COG, we anticipate that our goal of accruing 60 evaluable patients from those eligible is feasible within two years after Amendment #1 is activated. There are very few on-therapy cognitive intervention trials from which to base an estimate of feasibility, though at St. Jude Children's Research Hospital, recruitment to SJMB03, which has a reading-based intervention program embedded in the study, was strong. Specifically, 64% of children enrolled on the protocol have been randomized to either the treatment or standard-of-care arm of that protocol. The primary reasons that children were not randomized, in order of frequency, included 1) age outside the inclusion criteria, 2) poor medical status (including posterior fossa syndrome), 3) non-English speaking, and 4) parents did not consent to randomization ([name], study PI, personal communication on Oct. 29, 2010). We anticipate that parents of children receiving cranial radiation therapy will be aware of the potential risks of neurocognitive late effects, and that at least one quarter of these parents will be willing to have their children participate in a cognitive intervention trial, particularly since it is home-based. The project has the strong support of the Behavioral Sciences Committee, and we have identified key personnel at each site who can help to inform colleagues about the study and motivate referrals of eligible patients.

## 6.3 Statistical Analysis Methods

### 6.3.1 Endpoints

Primary endpoint is intervention compliance defined as at least 80% of sessions completed (i.e., completing at least 20 sessions within 9 weeks of starting training). The target is to have at least 75% of the participants compliant with intervention.

Secondary endpoints on subjective and objective measures of attention and WM include parent-rated executive function and WM using the Metacognition subscales from the BRIEF, the measure of executive function using the Groton Maze Learning task of the CogState battery and measure of WM by the one-back task from CogState. In addition, for participants who have participated in the optional psychologist-administered battery, we will analyze the measure of WM using Digit Span from Wechsler Intelligence Scales, measures of verbal and visual memory using Dot Location from Children's Memory Scale Spatial Span from Wechsler Scale.

Secondary endpoints on feasibility are the item responses to the 13-item Feasibility Interview assessing technical feasibility, adherence, satisfaction and ease of use.

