### 1.2 Exploratory Objective

To estimate the effect size of this program on measures of attention and working memory in patients with brain tumors treated with CRT in order to design a definitive large-scale clinical trial.

Hypothesis: Participants will show increases in attention and working memory compared to participants in the active control group, as measured by both objective and subjective measures of attention and working memory following completion of the intervention. Moreover, participants will maintain increased attention and working memory scores at a 6-month follow-up assessment.

[figure not shown]

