#### 4.3 Procedures

Three study visits will be required for participation in the study (see [Section 4.7](#)). First is the screening/baseline assessment, which will be conducted for all participants following study enrollment. The baseline testing must be performed within 4 months after the completion of CRT. The two remaining study visits are the post-intervention assessment and the follow-up assessment, which will be needed only for participants who meet criteria for randomization and who are randomized. Screening/baseline assessment may include administration of an abbreviated intellectual test battery, a WM battery, and a computerized attention measure (see [Appendix III](#)). Parents will complete questionnaire measures regarding their child's adaptive, behavioral, emotional, and attentional functioning. Clinical interviewing will be conducted to clarify any potential problems identified on the questionnaires; final decisions about psychosocial eligibility of children will be made by the evaluating psychologist at each site based on all available data. Participants and their parents will each receive a \$15 gift card (or comparably valued prize/compensation) for participation in the screening/baseline assessment. It is anticipated that some children who complete the screening/baseline assessment will not meet randomization criteria based on evidence of

intellectual disability or psychiatric functioning. In the trial of *Cogmed* with survivors, less than 10% of children screened were excluded from participation for these reasons.

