##### 4.5.3 Post-Intervention and 6-month Follow-up Assessments

**CogState**, a brief, computerized assessment of memory functioning will be administered following the intervention (at approximately 5 months post-CRT) and again 6 months following the completion of the intervention. The computerized testing can be administered by any individual who completes online training for CogState or who has already completed online training for any of the other COG trials for which CogState has been used (i.e., AAML1331, AALL1131, ACCL0922). Parents/caregivers will also be asked to complete the BRIEF and the Feasibility Interview at these timepoints. Testing will require approximately 20-30 minutes at each timepoint. The child will also complete the Feasibility Interview

at the post-intervention assessment, and the parent will complete the Computer Use questionnaire and ABAS-3 at the 6-month follow-up.

**Optional Testing:** It is highly recommended that the psychologist-administered measures also be administered, if possible, following the intervention (at approximately 5 months post-CRT) and again 6 months following the completion of the intervention. Measures were selected to be compatible with COG ALTE07C1, when possible, in order to be consistent with the Behavioral Science Committee's resolution to streamline assessments, promote higher compliance with neurocognitive study aims, reduce costs, and increase the ability to compare findings across COG-supported studies. The psychologist-administered post-intervention assessments will require about 30 minutes each. At each institution, a psychologist or neuropsychologist will oversee this optional testing.

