### 6.3.3 Analysis Plan

Compliance rate (the portion of patients who complete at least 80% of the sessions within 9 weeks) will be calculated for the overall study population and each arm separately. Z-test for binomial proportion with continuity correction will be used to examine if the overall compliance rate is lower than the target of 75%. Confidence intervals of the estimated compliance rate will be constructed for the overall study population and for each arm separately. We will use Fisher's exact test to examine if there is any significant difference in the compliance rate between the 2 arms. Compliance data on the number of sessions completed for all patients and for patients on each arm will also be described by summary statistics such as mean or median, and compared between the 2 arms by two-sample t-test or Wilcoxon rank sum test. We will use descriptive and summary statistics to report parent and child ratings of the intervention's technical feasibility, ease-of-use, and satisfaction across the three time-points that this information is collected. In addition, we will use descriptive and summary statistics to detail the total number of patients enrolled, determine rates and reasons for non-eligibility and patient refusal for randomization, characterize socioeconomic status of the parents and computer usage for the patients and evaluate the number and type of adverse incidents reported through the questionnaires (if any). We will use a series of t-tests (for continuous variables) and Chi-square tests or Fisher's exact tests (for non-continuous variables) to examine potential differences between eligible patients who accept or decline to be randomized to the treatment phase, between participants who are compliant (i.e., 80% of sessions completed) and noncompliant, and for other medical, psychosocial, and contextual factors.

The analysis of preliminary efficacy will be conducted on an intent-to-treat basis. We will use descriptive/summary statistics to summarize the objective and the subjective measures of attention and WM in each arm and the differences between the 2 arms on the post-intervention/6-month assessment or on the difference between the post-intervention/6-month assessment and the baseline assessment. Linear regression models using the post-intervention/6-month assessment as outcome will also be used to estimate the effect size of intervention with adjustment for potential confounders including the baseline assessment. Linear

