### APPENDIX III: STUDY ASSESSMENT INSTRUMENTS

**Note:** Study measures were chosen to overlap with those used in ALTE07C1, with the addition of the computerized CogState battery, which was chosen given its ability to be administered repeatedly over short intervals with negligible practice effects. The measure assigned initially by age will be used during the study even if the patient could move up to the next age level.

IQ*	Attention/ Working Memory	Verbal Memory	General	Parent Report
WISC-V** (Block Design Vocabulary)	CogState	CVLT-C**	Feasibility Interview	Feasibility Interview
	CMS** (Dot Location and Faces)			BASC-3*
	WISC-V** (Digit Span, Coding, Symbol Search, and Spatial Span subtests)			BRIEF
	Instructional WM**			ABAS-3
				BIS
				Socioeconomic Status Measure*
				Computer Use Questionnaire
				COG Language Preference Questionnaire

\* Baseline only

\*\* Optional psychologist-administered measure

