**CogState** is a computerized testing software package that offers a range of semi-automated assessment modules for individuals aged 6-90 ([www.cogstate.com](http://www.cogstate.com)). The software can be installed on most computer systems and can be proctored by a research assistant with minimal training. Data are automatically uploaded, scored, and stored. Test batteries can be fully customized, and include tasks tapping visual motor, processing speed, visual attention, visual and verbal learning and memory, and working memory. A battery suitable for evaluating the core neurocognitive processes affected by cancer treatment would take between 12-18 minutes. Reliability is .77 with no practice effects when testing intervals are greater than one month. Age-based standard scores (mean = 100, SD 10) are computed for each task based on a normative sample of several hundred individuals. CogState tasks have been used successfully in trials of populations relevant to pediatric cancer patients. Specifically, it has been used with attention deficit hyperactivity disorder participants, for which CogState tasks discriminate between those with and without the diagnosis, and those on and off medication, as well as typically-developing children. In addition, CogState has been used in samples of patients with concussions, HIV/AIDS, pediatric cerebral malaria, and adult cancer patients. CogState is also currently being used in a multi-site trial funded by NCI to examine neurocognitive symptoms in long-term survivors of pediatric cancer. CogState will be administered at all time points.

**Instructional Working Memory Task** (Instructional WM). The Instructional WM is a brief task administered to children to evaluate functional application of WM skills. Children are asked to use task props (e.g., pencils, folders, etc.) to follow an increasingly complex set of instructions. For example, a child might be asked to “Pick up the blue ruler and put it in the red folder”. Scores are calculated based on a combination of accuracy in following the instructions weighted by how many actions the child is asked to perform with a single command. The instructional WM will be administered at all time points for sites that have a psychologist to administer these measures.

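### Is the exploratory attention effect left open to choice because no score in Section 6.3.1 is labelled attention?

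*Combined protocol and SAP*

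**What the plan says.** Section 1.2 sets an exploratory objective: an effect size on attention and WM to help design a definitive trial. Its hypothesis expects gains "as measured by both objective and subjective measures of attention and working memory following completion of the intervention".

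Section 6.3.1 takes up the same pairing: "Secondary endpoints on subjective and objective measures of attention and WM include parent-rated executive function and WM using the Metacognition subscales from the BRIEF", followed by "the measure of executive function using the Groton Maze Learning task of the CogState battery and measure of WM by the one-back task from CogState". For sites that run the optional psychologist battery it adds Digit Span, Dot Location and Spatial Span.

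Other sections describe the instruments more loosely:

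- Section 4.3, on the baseline visit: "Screening/baseline assessment may include administration of an abbreviated intellectual test battery, a WM battery, and a computerized attention measure". It adds that parent questionnaires cover attentional as well as adaptive, behavioral and emotional functioning.
- Section 4.5.3 describes CogState as "a brief, computerized assessment of memory functioning will be administered following the intervention".
- Appendix III places CogState, the CMS subtests, four WISC-V subtests and the Instructional WM task in one column headed "Attention/ Working Memory". It says CogState batteries can be customized and "include tasks tapping visual motor, processing speed, visual attention, visual and verbal learning and memory, and working memory".
- Section 6.3.3 will "summarize the objective and the subjective measures of attention and WM in each arm", give differences between arms, and estimate effects by regression that includes the baseline value. Mixed models will also be considered.

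**The concern.** An objective that names attention should lead to a score that measures it. Here the objective and the list heading name attention, but every label under the heading says executive function, WM or memory. The two descriptions of the computerized test also differ: attention in Section 4.3, memory functioning in Section 4.5.3. The CogState task list for this study is not in the documents, so a reader cannot tell whether an attention task is switched on.

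If nobody has said which score carries the attention effect, someone could look at several scores at two time points and present the most favourable as the attention result. That would bias the estimate upward. Because the estimate is meant to help plan the next trial, an inflated value could make that trial too small.

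**Working it through.** **The plan's only power figure.** It concerns compliance (Section 6.3.2): n = 60, target 0.75, alternative 0.59, one-sided 0.05, Z-test with continuity correction.

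- Cut-off = 0.75 − 1.645 × √(0.75 × 0.25/60) − 1/120 = 0.650.
- Power = Φ[(0.650 − 0.59)/√(0.59 × 0.41/60)] = 0.827, against 0.82 stated.

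The figure reproduces, and nothing in this point touches it.

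**Labels, side by side.**

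| Score or task | Label in 6.3.1 | Appendix III column |
|---|---|---|
| BRIEF Metacognition | executive function and WM | parent report |
| CogState Groton Maze | executive function | joint attention/WM |
| CogState one-back | WM | joint attention/WM |
| Digit Span | WM | joint attention/WM |
| Dot Location | verbal and visual memory | joint attention/WM |
| Spatial Span | verbal and visual memory | joint attention/WM |

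These are six scores or tasks from four instruments (BRIEF, CogState, Wechsler, CMS). Individually labelled attention: 0 of 6. In the joint column: 5 of 6. The Spatial Span label comes from a sentence that lacks a connective, and Appendix III calls that subtest working memory. Neither reading is attention.

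**How large selection could be, if it happened.** Assume 30 per arm, no true effect, complete data, one time point, and correlation between scores of 0 to 0.5 (the documents give none).

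- SE of d ≈ √(2/30) = 0.258.
- Expected largest of 2 scores: 0.146 at correlation 0 and 0.103 at 0.5.
- Expected largest of 5 scores: 0.300 at correlation 0 and 0.213 at 0.5.
- Baseline adjustment, using the CogState reliability of 0.77 (Appendix III) as the baseline correlation for every score, multiplies by √(1 − 0.77²) = 0.638. This gives 0.093 and 0.066 for 2 scores, and 0.192 and 0.136 for 5.
- Against the pilot attention effect of d = 0.52 (Section 2.3.2): 0.066/0.52 = 13% and 0.300/0.52 = 58%.

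Five is the overlap between the joint column and Section 6.3.1, not the size of the column. The column also holds Faces, Coding, Symbol Search and Instructional WM, so it has at least 2 + 2 + 4 + 1 = 9 scores, counting two for CogState. More candidates or a second time point would raise the figure. The range therefore illustrates a mechanism and does not measure a harm in this trial.

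**Does the plan contain that mechanism?** Section 6.3.3 summarises the measures in each arm, compares the arms and fits regressions. It has no step that selects one score. Presenting one-back or Digit Span as the attention effect would contradict Section 6.3.1, which calls both WM. With all six reported under those labels, the expected value of each under no effect is 0, and a reader sees the whole set.

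**The case for a change.** The strongest case for a change starts from the pilot. Section 2.3.2 reports attention (d = 0.52), WM (d = 0.46) and parent-rated attention problems (d = 0.50) as three separate results, so the investigators do distinguish the constructs. The instruments it names, the Wide Range Assessment of Memory and Learning and the Conners-3, are not in Table 1, so the pilot offers no default. The list in Section 6.3.1 is worded as open-ended. There are two post-baseline time points and several permitted models. After baseline, parents complete only the BRIEF and, at 6 months, the ABAS-3 among the rating scales, and neither is described as an attention scale. Naming a score would cost little and would be more credible before the data are seen than after.

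Much of this is fair. The labelling is loose, and a planner who wants a result for attention alone cannot find it by name. But an open list does not release the analysts from reporting the scores that are named, and Section 6.3.3 reports measures without choosing among them. The parent side is less bare than it looks: Section 4.3 includes attentional functioning among the areas covered by the baseline questionnaires. That set contains the BRIEF, which is repeated at both later visits, although the plan does not say which questionnaire covers attention.

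The possible amendments also gain little. Naming a CogState attention score depends on a task list that the documents do not show. Narrowing Section 1.2 to executive function and WM would alter a phrase and no result.

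**Conclusion.** The observation is accurate: no individual score in Section 6.3.1 is labelled attention, and the sections describe the computerized test differently. It is a gap in labelling on an exploratory objective with no power claim. The plan treats attention and WM as one joint domain, and analysts can fill the gap sensibly by reporting each named score as what it is, adjusted for its baseline.

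The 13% to 58% inflation should not be read as an expected bias. It rests on assumed correlations, on one reliability applied to all tests, on full data for optional tests, and above all on a selection that Section 6.3.3 does not provide for.

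The conclusion assumes that the named scores are all reported under the labels of Section 6.3.1. Section 4.1 also calls attention and WM primary outcomes. That is a separate wording slip, since Sections 1.1, 6.2, 6.3.1 and 6.3.2 make feasibility and compliance primary. No change to the plan is needed.
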